Several risk factors have been identified to cause temporary hypocalcaemia post-total thyroidectomy and common causes include accidental parathyroid removal and disruption of blood supply to the parathyroid glands. The treatment of symptomatic hypocalcaemia is intravenous infusion of calcium gluconate. There is limited data on the prophylactic use of intravenous calcium gluconate in preventing or reducing the rate of hypocalcaemia. A prospective cohort study by Urono, *et al* in 2006 showed that a significantly lower rate of post-total thyroidectomy hypocalcaemia was achieved by giving prophylactic infusion of calcium solution within 3-8 hours after surgery. The serum calcium level for the intervention group on the first post-operative day was 7.91 +/- 0.49 mg/dL while in the control group it was 7.65 +/- 0.54 mg/dL. There was no difference in the serum intact parathyroid hormone (i-PTH) level in both groups on the first post-operative day. This was the first prospective study that evaluated the role of prophylactic calcium infusion in reducing the rate of hypocalcaemia after total thyroidectomy².

Hafez, *et al* in the year 2014 found that in a randomized controlled trial involving 40 patients, prophylactic intravenous infusion of calcium gluconate during total thyroidectomy was effective in minimizing the risk for post-operative symptomatic hypocalcaemia³. These are the research currently available on the role of prophylactic intravenous calcium gluconate infusion after total thyroidectomy. Multiple factors can influence the rate of post-operative hypocalcaemia including patient characteristics or surgical technique. Rio PD, *et al* reported that females are at double risk of developing hypocalcaemia as compared to the male gender. Apart from that, the total thyroidectomy group have higher rates of hypocalcaemia as compared to the sub-total thyroidectomy group⁴. Total thyroidectomy plus central nodes dissection will increase the rate of post-operative hypocalcaemia even further as compared to total thyroidectomy alone (44% vs 14.3% of laboratory proven hypocalcaemia)⁷.

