Clinically, neuromuscular irritability can be demonstrated by eliciting Chvostek's or Trousseau's signs. Chvostek's sign is elicited by tapping the skin over the facial nerve anterior to the external auditory meatus. Ipsilateral contraction of the facial muscles occurs in individuals with hypocalcaemia. It has to be noted that Chvostek's sign is also present in 10% of normal individuals¹⁵. Trousseau's sign is elicited by inflation of a blood pressure cuff to 20 mm Hg above the patient's systolic blood pressure for 3-5 minutes. Carpal spasm presents as flexion of the wrist and of the metacarpal phalangeal joints, extension of the interphalangeal joints, and abduction of the thumb. Cardiac manifestations such as prolonged QT interval, abnormal T wave and cardiac arrhythmias could be one of the features of acute hypocalcaemia. Thus, by classifying hypocalcaemia into mild or severe, depending on the clinical symptoms and biochemical results can be useful to direct treatment strategy (**Appendix 3**).

Calcium gluconate is the intravenous calcium salt of choice to correct hypocalcaemia as calcium chloride often causes local irritation. In most hospital settings, only calcium gluconate is readily available. Calcium gluconate contains 90 mg of elemental calcium per 10 mL ampoule, and usually 1 to 2 ampoules (180 mg of elemental calcium) diluted in 50 to 100 mL of 5% dextrose is infused over 10 minutes. This can be repeated until the patient's symptoms have resolved. With persistent hypocalcaemia, administration of a calcium gluconate infusion over a longer period of time may be necessary. Infusion rates of 0.5-2.0 mg/kg/hour are recommended¹⁵.

The most common adverse effects of intravenous calcium infusion are hypertension, nausea, vomiting, and flushing. Bradycardia and heart block may occur in rare cases. Patients receiving intravenous calcium should be placed on cardiac monitoring and administration should be discontinued if bradycardia ensues. Patients may complain of tingling sensation, a sense of oppression or heat wave and a calcium or chalky taste following administration of intravenous calcium gluconate. As extravasated calcium may cause severe tissue irritation and necrosis, it should be given through a well-functioning intravenous catheter^{16,17}.

Objectives

Primary Objectives

- To determine whether prophylactic infusion of calcium gluconate reduces the rate of early hypocalcaemia after total thyroidectomy as compared to placebo treatment

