Secondary Objectives

- To determine whether prophylactic infusion of calcium gluconate reduces the length of hospital stay as compared to placebo group

Study Endpoint

- The level of corrected calcium in the first 48 hours after total thyroidectomy between intervention and control group

Hypothesis

- Null hypothesis: prophylactic infusion of calcium gluconate does not reduce post-total thyroidectomy hypocalcaemia and length of hospital stay as compared to placebo group
- Alternative hypothesis: Prophylactic infusion of calcium gluconate reduces the rate of post-total thyroidectomy hypocalcaemia in the first 48 hours and shorten the length of hospital stay as compared to placebo group

Methodology

Current Protocol in UMMC

All patients admitted or scheduled for total thyroidectomy in UMMC will have their baseline serum calcium and i-PTH levels checked one day before surgery. Subsequently, all patients will have their serum calcium levels checked at the 6-hour, 12-hour, 24-hour, 36-hour and 48-hour mark post-surgery. The i-PTH level will be tested at the 12-hour post-surgery mark together with the serum calcium level. Oral calcium supplements 2g a day (Calcium Carbonate 1g b.d.) and Rocaltrol 0.25mcg o.d. will be started once the patients are able to tolerate orally. If a patient experiences symptoms of hypocalcaemia and the serum calcium level is less than 2.0mmol/L, the patient will be administered a rescue dose of intravenous calcium gluconate (3g of calcium gluconate in 50mls of normal saline) over 4 hours duration. However, if a patient experiences hypocalcaemia symptoms and the serum calcium level is more than 2.0mmol/L, the patient will be continued on oral supplements at an increased dosage (3-4g of calcium carbonate a day). The usual hospital stay for a total thyroidectomy patient is 48 hours post-surgery. If a patient is asymptomatic and the serum calcium level is normal at 48-hours post-surgery, the patient can be discharged with an appointment at the outpatient clinic in two weeks time.

Study Type and Design

This is a single centre, double blinded and prospective randomized controlled trial which will be conducted in University Malaya Medical Centre (UMMC), Endocrine Surgery Unit. The duration of the study will be from June 2020 until May 2022 (2 years duration).

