Patient will be recruited from the endocrine surgery outpatient clinic and in-patient referrals for total thyroidectomy. There are several inclusion and exclusion criteria for recruitment into this study. After fulfilling the inclusion criteria, patients will be required to give consent and agree to participate in this study after explanation by the clinician and investigator in charge. Participants will be randomized into an intervention group (Group A) and a control group (Group B) with the ratio of 1:1 during admission for surgery (**Appendix 2**). The method of randomization utilised will be random randomization. Both the surgeon and patient will not be aware of the randomization arm of any particular patient. Only the primary investigator and assistants will be aware of the randomization of a patient. Before surgery, baseline serum calcium, magnesium and i-PTH will be obtained. If intra-operatively, all 4 parathyroid glands are accidentally removed during the total thyroidectomy, these patients will be excluded from the study as this will definitely affect their serum calcium levels post-surgery.

After total thyroidectomy, the intervention group will receive a calcium gluconate infusion over one hour (1g of intravenous calcium gluconate, diluted in 100mls of normal saline) within 4 hours after skin closure. On the other hand, the control group will receive a saline infusion (100 ml of normal saline) infused over one hour within 4 hours of skin closure. Both groups will be put on cardiac monitoring

during the administration of the intravenous infusion. The dosing, dilution and infusion rate for the calcium gluconate are within the safety limits as recommended by FDA and WHO model formularies.

Post-total thyroidectomy, both groups of patients will receive the same regime of oral calcium carbonate 1g t.d.s. and oral Rocaltrol 0.25mcg o.d. as per current protocol in the endocrine surgery unit. Serum calcium levels will be obtained at the 6-hour, 12-hour, 36-hour, 48-hour mark post-surgery. The blood samples collected will be sent to the biochemical laboratory of UMMC.

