In the endocrine surgery unit, the current practice is that all patients who had total thyroidectomy performed will be kept as an in-patient routinely for at least 48 hours so that their serum calcium levels can be monitored at the intervals mentioned above (6-hour, 12-hour, 24-hour, 36-hour & 48-hour). Therefore, this study will not incur an additional stay or prolonged admission.

Target Population

The target population is from the endocrine surgery clinic and UMMC ward. Target population consists of all patients scheduled for total thyroidectomy during the period of 1st June 2020 to 31st May 2022.

Sample Size

A pilot study will be conducted after obtaining approval from MREC (Medical Research Ethics Committee) UMMC. 10 patients will be recruited for the pilot study and randomized into 5 patients each arm. Sample size calculation will then be derived from the mean and standard deviation obtained from the pilot study.

Inclusion Criteria

- Age between 18-80 years old
- Scheduled for total thyroidectomy in UMMC

Exclusion Criteria

- Their age outside the range of 18-80
- Have parathyroid disorders or end stage renal failure
- On calcium or vitamin D supplements prior to surgery
- Have deranged calcium homeostasis pre-operatively (outside the normal range of 2.2-2.6 mmol/L)
- Scheduled for total thyroidectomy plus lymph node dissection

Withdrawal Criteria

Subjects can choose to withdraw at any time and withdrawn subjects will not be replaced.

Study Duration and Time-line (refer to Gantt Chart)

The total research period is from October 2019 till February 2023. The first two months will be spent on literature review of the relevant papers and the next two months will be on preparation of the research proposal. Subsequently, the research proposal will be submitted to MREC for approval.

After the proposal is approved by MREC, data collection will tentatively start from June 2020 till May 2022. Subsequently, data analysis will start from June 2022 till October 2022. Another two months will be spent on the final report writing and finally thesis presentation and submission on January to February 2023. (please refer to the Gantt chart)

Data Collection Tools and Techniques

As this is a prospective randomized controlled trial, relevant participants information and blood investigations will be recorded and documented in the Electronic Medical Record (EMR). These data will then be transcribed into SPSS for analysis.

Data Analysis

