Data recorded will be analysed using SPSS Statistics Version 25. Continuous data will be expressed as Mean \pm standard deviation unless otherwise stated. Paired T- test was used for comparison of paired samples. The students's T- test was used for comparison of continuous variables between different groups. Chi-square test will be used for categorical data analysis. A value of $P < 0.05$ will be considered statistically significant. The data collected will be analysed using an per-protocol analysis.

[figure not shown]
Risk and Benefit to Study Participants

The dose and infusion rate of calcium used in this study is within the safety limits proposed by the World Health Organization (WHO). The adverse effects of calcium infusion are rare and may range from mild to severe. Common adverse effects including nausea, vomiting, hypertension, flushing and local inflammation over the infusion site. Severe adverse effects such as heart block and slow heart rate may occur but are extremely rare with this regime and dosage of calcium infusion. All study participants will be placed on cardiac monitoring and administration will be discontinued if adverse effects supervene. None of the patients in the endocrine surgery unit, UMMC experienced

any adverse effect after receiving intravenous calcium gluconate in the year 2018 and 2019. Therefore, there is very minimal risk for subjects who choose to participate in this study.

In the other hand, this study does not present any direct benefit to the participants who involved in this study. However, information obtained from this study will help to formulate a better treatment protocol/plan to reduce and prevent incidences of hypocalcaemia after total thyroidectomy.

Flow Chart

Ethical Consideration of Study

This study will be conducted in compliance with ethical principles outlined in the Declaration of

Helsinki and Malaysian Good Clinical Practice Guideline.

Informed Consent

Eligible patients will be identified during clinic visits. Information regarding the study will be given and explained to them during clinic visit. They will be allowed to take the patient information sheet home and consult with their family members. Informed consent will be obtained when they are admitted for surgery.

Privacy and Confidentiality

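### The sample size is to come from the mean and SD of a 5-per-arm pilot, with no target difference or power stated; those estimates are too imprecise to size the trial.

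*Protocol*

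**What the plan says.** The Sample Size section of the protocol contains the whole sizing plan. It first sets up the pilot: "10 patients will be recruited for the pilot study and randomized into 5 patients each arm". It then gives the rule: "Sample size calculation will then be derived from the mean and standard deviation obtained from the pilot study". It states no N, power, target difference, dropout allowance, minimum N or safety margin on the SD.

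The Study Endpoint is a continuous measure: "The level of corrected calcium in the first 48 hours after total thyroidectomy between intervention and control group". The primary objective is a rate: "To determine whether prophylactic infusion of calcium gluconate reduces the rate of early hypocalcaemia after total thyroidectomy as compared to placebo treatment".

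The protocol reports figures that bear on sizing but does not use them for it. The Literature Review gives a published prospective cohort: "The serum calcium level for the intervention group on the first post-operative day was 7.91 +/- 0.49 mg/dL", against 7.65 +/- 0.54 mg/dL in its controls. The Introduction gives the unit's own rates of symptomatic hypocalcaemia within 48 hours: 40% in 2018 and 23% in 2019.

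**The concern.** A sample size rests on a difference worth detecting, chosen beforehand, and on a reasonably well-known SD or control rate. Here the only named source for these is 10 patients. An observed difference from 5 per arm is mostly noise. If it is large by chance, the main trial is too small to answer its question. If it is small by chance, the computed N cannot be recruited. If it points the wrong way, there is no sensible N at all.

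This is not detail deferred to an analysis plan. The protocol itself fixes the rule, and a later plan that did better would have to contradict it. Recruitment is limited to about two years at one centre, and withdrawn patients are not replaced, so a poor N is hard to repair later.

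**Working it through.** The protocol states no N or power, so there is no figure to reproduce. The check asks how well the rule performs.

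**Inputs from the protocol**
- Pilot of 5 per arm (Sample Size), so a pooled SD has 8 degrees of freedom.
- Allocation "with the ratio of 1:1 during admission for surgery" (Study Type and Design).
- Data Analysis: the Student's "T- test was used for comparison of continuous variables between different groups"; a P value below 0.05 "will be considered statistically significant". Sidedness is not given.

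**Assumptions**
- Two-sided alpha 0.05, 80% power, normal data, equal SDs.
- True effect of 0.5 SD. This is close to the cited cohort: difference 7.91 - 7.65 = 0.26 mg/dL; pooled SD = sqrt((0.49² + 0.54²)/2) = 0.516; ratio 0.504.

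**Step 1. N needed.** n per arm = 2(1.960 + 0.842)²/d² = 2 × 7.849/0.25 = 62.8, so 63.

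**Step 2. Precision of the pilot.**
- Difference: t(0.975, 8 df) × sqrt(2/5) = 2.306 × 0.632 = 1.46 SD either way. On the cohort's scale the standard error is 0.516 × 0.632 = 0.326 mg/dL, larger than the 0.26 mg/dL effect itself.
- SD: sqrt(8/chi-square) at the 97.5% and 2.5% points gives 0.68 and 1.92 times the estimate. N depends on the SD squared, so this alone multiplies N by 0.46 to 3.67.

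**Step 3. Wrong sign.** P = Φ(-0.5/0.632) = Φ(-0.79) = 21%.

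**Step 4. Computed N when both the difference and the SD come from the pilot.** Draw the difference from N(0.5, 0.4) and the variance from chi-square(8)/8, and put them into n = 2 × 7.849 × s²/diff². The thresholds are about half of 63 and twice 63.

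| Pilots counted | N below 32 per arm | N above 126 per arm |
|---|---|---|
| All, using the size of the difference whatever its sign | 42% | 31% |
| Right sign only | 49% | 24% |

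Over all pilots, N lands within 25% of the required value in only about 10%. True power at a given N is Φ(0.5 × sqrt(n/2) - 1.96). Among right-sign pilots its median is about 53%, and about 65% of those trials have less than 80% power.

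**Step 5. Computed N when only the SD comes from the pilot** and the difference is fixed at the true 0.5 SD. The 5th to 95th percentiles are 22 to 122 per arm. N is below 32 in 14% and above 126 in 4%. Median power is about 77%, and about 56% of trials fall below 80%.

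**Step 6. Sensitivity to the assumed effect.** With both quantities from the pilot, N is within 25% of the required value in 6% of pilots at a true effect of 0.2 SD and 13% at 0.8 SD.

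**Step 7. What candidate inputs would give, before dropout.**
- Calcium level, cohort figures: 2 × 7.849 × 0.516²/0.26² gives 62 per arm at 80% power; 83 at 90%.
- Rate, assuming for illustration that it is halved, pooled-variance formula at 80% power: 40% to 20% gives (1.270 + 0.532)²/0.20² = 82 per arm; 23% to 11.5% gives (1.047 + 0.444)²/0.115² = 169 per arm.

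**The case against.** The strongest reply is about wording. The protocol names a mean and a standard deviation; it does not say that the observed between-arm difference becomes the target effect. A reader might infer that it does, and a two-arm pilot, a between-group t-test and no stated target difference make this the likelier reading. It remains an inference, and the figures in steps 3 and 4 depend on it. Under the SD-only reading the wrong-sign problem disappears, and it would be too strong to call N close to random. What survives is still poor: a more than fivefold range in N, and more than half of trials underpowered.

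The simulation also applies every computed N mechanically. In practice, very small or unrecruitable values would be overridden. That is fair, but the protocol states no rule for doing so.

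A reader might infer that pilot patients will be pooled into the final analysis and that the type I error suffers. The protocol does not say whether they are. Without pooling, a poor N costs power only.

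A reader might also take the cohort and unit figures as ready-made replacements. The protocol does not support that. The cohort was a prospective cohort study of a calcium solution given 3-8 hours after surgery, measuring first-day serum calcium that is not stated to be corrected. This trial excludes lymph node dissection and abnormal baseline calcium. The unit's rates are for symptomatic hypocalcaemia, carry no denominators, and the protocol does not say how they were compiled. The 33% reported for 2019 is a rescue-infusion rate and should not be read as a hypocalcaemia rate.

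Finally, a mean and SD are the right kind of input for the stated continuous endpoint. That the primary objective is a rate is a separate inconsistency and adds no weight to this point.

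**Conclusion.** The concern holds in this form: the protocol fixes a sizing rule that rests on 10 patients, states no target difference or power, and so appears to draw both the effect and the SD from them.

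On that reading, with a true effect of 0.5 SD, the computed N misses the required 63 per arm by a factor of two or more in roughly three pilots out of four (42% + 31% = 73%). When the sign is right, the typical trial has about 53% power. On the SD-only reading the damage is smaller, but a majority of trials still fall short of 80%.

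The figures assume two-sided alpha 0.05, 80% power, normal data and equal SDs. The conclusion on the likelier reading does not depend on the 0.5 SD effect, since it holds at 0.2 and 0.8 SD as well. The documents do not support a claim that the final test is invalid, nor that the protocol already contains the correct inputs.

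**What to change.** Replace the rule in the Sample Size section with text to this effect:

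- The sample size is based on a minimum worthwhile difference set in advance, two-sided alpha 0.05 and a stated power.
- The SD (for calcium level) or the control rate (for the rate objective) comes from data larger than the pilot. The cited cohort's SD of 0.49-0.54 mg/dL and the unit's symptomatic rates of 40% and 23% are candidate inputs. Their limits are stated (different infusion, population and definition; no denominators given), and N is shown over a range.
- The 10-patient pilot tests feasibility only; its between-arm difference is not used for sizing.
- If the two-year window fixes the number of patients, the power at that number is stated.

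The cost is a recalculation and a paragraph of text. The downside is that the stated power may be less favourable than one computed from a lucky pilot.

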Appendix

Appendix 1
